9.4.4 SAFETY ANALYSES

Safety endpoints will be analyzed as summary statistics during treatment, coded as per Medical Dictionary for Regulatory Activities and counted once only for a given participant. Start/stop dates, severity as determined by the investigator, relationship, expectedness, outcome and duration will be reported. Adverse events leading to premature discontinuation from the study and serious treatment-emergent AEs will be presented separately in a listing.

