6.1.2 DOSING AND ADMINISTRATION

Each participant will be started at 80 IU subcutaneously 2-3 weekly and the dosing increased to up to three times weekly at the discretion of the primary investigator. The dosing will remain consistent unless the investigator decides to reduce or escalate the dosing at the one month mark. The dosing may be stopped altogether and the subject followed only for safety in the event of uncontrolled hypertension, blood sugar, glaucoma or other serious adverse events in the opinion of the investigator. The dosing of study drug will continue for 12 weeks.

Missed or delayed doses should be taken as soon as realized unless it would result in two doses being given at once, in which case the investigator should be contacted for a modified dosing schedule.

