7 STUDY INTERVENTION DISCONTINUATION AND PARTICIPANT DISCONTINUATION/WITHDRAWAL

7.1 DISCONTINUATION OF STUDY INTERVENTION

Discontinuation during study does not mean discontinuation from the study, and remaining study procedures should be completed as indicated by the study protocol. If a clinically significant finding is

identified (including, but not limited to changes from baseline) after enrollment, the investigator or qualified designee will determine if any change in participant management is needed. Any new clinically relevant finding will be reported as an adverse event (AE).

The data to be collected at the time of study intervention discontinuation will include the following:

- Subject rated assessment of eye dryness, use of concomitant medications since last visit, occurrence of AEs since last visit, unused investigational product will be collected, BCVA, slit lamp biomicroscopy, iop, dilated fundus exam and pregnancy test for women of childbearing potential.

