8.3.4 TIME PERIOD AND FREQUENCY FOR EVENT ASSESSMENT AND FOLLOW-UP

Describe how AEs and SAEs will be identified and followed until resolved or considered stable. Specify

The occurrence of an adverse event (AE) or serious adverse event (SAE) may come to the attention of study personnel during study visits and interviews of a study participant presenting for medical care, or upon review by a study monitor.

All AEs including local and systemic reactions not meeting the criteria for SAEs will be captured on the appropriate case report form (CRF). Information to be collected includes event description, time of onset, clinician's assessment of severity, relationship to study product (assessed only by those with the training and authority to make a diagnosis), and time of resolution/stabilization of the event. All AEs occurring while on study must be documented appropriately regardless of relationship. All AEs will be followed to adequate resolution.

Any medical condition that is present at the time that the participant is screened will be considered as baseline and not reported as an AE. However, if the study participant's condition deteriorates at any time during the study, it will be recorded as an AE.

Changes in the severity of an AE will be documented to allow an assessment of the duration of the event at each level of severity to be performed. AEs characterized as intermittent require documentation of onset and duration of each episode.

The study coordinator will record all reportable events with start dates occurring any time after informed consent is obtained until 7 (for non-serious AEs) or 30 days (for SAEs) after the last day of study participation. At each study visit, the study coordinator will inquire about the occurrence of AE/SAEs since the last visit. Events will be followed for outcome information until resolution or stabilization.

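### The AE listing in 9.4.4 is triggered by leaving the study, so it does not identify AEs that stopped the drug, and the summary window is undefined

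*Protocol*

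**What the plan says.** Section 9.4.4 of the protocol sets the safety analysis. On timing it says: "Safety endpoints will be analyzed as summary statistics during treatment". Each event is counted once per participant, and among the attributes shown, "relationship, expectedness, outcome and duration will be reported". On listings it says: "Adverse events leading to premature discontinuation from the study and serious treatment-emergent AEs will be presented separately in a listing".

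Three other sections bear on this:

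- Section 6.1.2 foresees an end to all dosing, with "the subject followed only for safety in the event of uncontrolled hypertension, blood sugar, glaucoma or other serious adverse events". It also lets the investigator change the dosing at the one-month mark.
- Section 7.1 separates stopping drug from leaving: "Discontinuation during study does not mean discontinuation from the study, and remaining study procedures should be completed".
- Section 8.3.4 collects events from consent "until 7 (for non-serious AEs) or 30 days (for SAEs) after the last day of study participation".

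Neither 'during treatment' nor 'treatment-emergent' is defined in either document. The SAP is a single paragraph on change from baseline in completers and has no rule for adverse events.

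**The concern.** In this design the foreseen response to intolerance is to stop the drug and keep following the participant. The discontinuation listing responds to a different event, departure from the study. A participant who takes the route in 6.1.2 does not meet that criterion, so the AE that ended dosing is not shown as having done so.

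Safety is a stated objective in the synopsis and in section 3, and section 4.2 presents the study as a possible basis for a larger controlled trial. The number of people who had to stop or reduce the drug is one of the main tolerability results such a pilot can pass on. With about 12 participants, one or two cases change the picture.

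The second issue is the window. Events are collected beyond the last dose, but the plan does not say whether they enter the summary, or whether a serious event after the last dose counts as treatment-emergent.

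**Working it through.** **No figure to reproduce.** Section 9.2 sets 12 completing participants without an AE rate or power. The check is therefore a comparison of sections and a count of days.

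**Step 1: where an AE that stops dosing appears.** Take a participant whose AE begins on drug, whose dosing is then stopped, and who stays for follow-up.

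- Summary in 9.4.4: counted, since onset is on drug under any reading.
- Listing, discontinuation criterion: not met, because under 7.1 the participant has not left the study.
- Listing, serious criterion: met only if the AE is serious and treatment-emergent, and then shown without its link to dosing. A non-serious AE is not listed.
- Elsewhere: section 7.2 records on the CRF the reason for leaving the study. The data that 7.1 requires when drug is stopped include AEs since the last visit, but not the reason for stopping. Section 8.3.4 says "Information to be collected includes event description, time of onset" and goes on to severity, relationship and resolution; action taken with study drug is not named there or in 9.4.4. Section 9.4.8 rules out individual listings by measure and time point.

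So the event is kept, but its role in ending dosing is not shown in any planned output.

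**Step 2: illustration of size.** The documents give no rate of drug discontinuation, so the number who stop drug for an AE but stay is an assumption. Denominator 12, exact (Clopper-Pearson) 95% intervals:

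| Stop drug, stay in study | Found by the planned discontinuation criterion | Found by a criterion on drug discontinuation |
|---|---|---|
| 0 | 0/12 | 0/12 = 0% (0 to 26.5%) |
| 1 | 0/12 | 1/12 = 8.3% (0.2 to 38.5%) |
| 2 | 0/12 | 2/12 = 16.7% (2.1 to 48.4%) |
| 3 | 0/12 | 3/12 = 25.0% (5.5 to 57.2%) |

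**Step 3: collection days after the last dose.** Inputs: 12 weeks of dosing (6.1.2) = 84 days; final visit at Day 84 (schedule of activities), taken as the last day of participation; 7 or 30 further days (8.3.4). Counting from Day 1, collection runs 84 + 7 = 91 days for non-serious AEs and 84 + 30 = 114 days for SAEs. Days after the last dose = total − day of last dose. The early stop days are assumptions; Day 28 stands for the one-month mark.

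| Last dose | Non-serious AEs | SAEs |
|---|---|---|
| Day 84 | 91 − 84 = 7; 7/91 = 7.7% | 114 − 84 = 30; 30/114 = 26.3% |
| Day 56 | 35/91 = 38.5% | 58/114 = 50.9% |
| Day 28 | 63/91 = 69.2% | 86/114 = 75.4% |
| Day 14 | 77/91 = 84.6% | 100/114 = 87.7% |

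The Day 84 row holds whether 'during treatment' means on drug or the planned 12 weeks. The other rows apply only if it means on drug. If it means the planned 12 weeks, an early stop adds nothing and the figures stay at 7/91 and 30/114.

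**The case against.** A reader might infer that AEs which stop or reduce dosing disappear from the safety result. The documents do not support that. Such an AE normally starts on drug and is summarised with its severity, relationship and outcome. Section 6.1.2 also speaks of other serious adverse events after naming hypertension, blood sugar and glaucoma, which suggests that those conditions are regarded as serious. If so classed and treatment-emergent, they reach the listing by its second criterion. This stands, and it limits the point to the missing link with dosing and to non-serious AEs.

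A reader might also infer that post-dose events are certainly excluded, for example that a stop at Day 28 removes 84 − 28 = 56 of 84 study days (67%). That holds on only one reading of an undefined term; on the 12-week reading it is zero. The SAE listing is governed by 'treatment-emergent', which could include a post-dose window. What can be said is that these events have no stated place.

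Three further objections have some force:

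- Section 7.2 allows the investigator to withdraw a participant for an AE, or when study drug cannot be received for 14 days. Anyone withdrawn because of an AE would be listed. The 0 of 2 applies to those who stay, as 6.1.2 and 7.1 intend.
- Section 9.4.3 summarises IOP at every visit in all who were dosed, so a pressure signal has another output. That output still does not show that dosing was stopped.
- The CRF is not among the documents, and the list in 8.3.4 is not exhaustive. It cannot be claimed that action taken is not collected, only that neither section names it.

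Section 6.1.2 does not tie dose reduction to an AE, so the case for listing reductions is weaker than that for stops.

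**Conclusion.** The point holds in limited form. The discontinuation criterion in 9.4.4 does not fit a design in which drug can be stopped for an AE while the participant stays. Followed as written, the report could show no AEs leading to discontinuation although dosing was stopped for toxicity. The 0 of 2 is an illustration resting on an assumed number who stop and stay, not a forecast.

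The window defect is one of definition. At least 7 of 91 collection days for non-serious AEs and 30 of 114 for SAEs lack a stated place in the summary, assuming a full course and last participation at Day 84. These are shares of days, not of events. SAE reporting to the sponsor under 8.3.6 is unaffected; the gap is in tabulation and listing. This is a cheap improvement worth making, not a flaw that undermines the study.

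**What to change.** In section 9.4.4:

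1. Change the listing criterion to: AEs leading to discontinuation or reduction of study drug, or to discontinuation from the study.
2. Define the summary window as first dose to the end of the collection periods in 8.3.4, and show events on drug and events after the last dose separately.
3. List all SAEs over that period.

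In section 8.3.4, name action taken with study drug among the items recorded with each AE, and check that the CRF has the field. This should be in place before data collection, because the link between an AE and a dose change may be hard to reconstruct afterwards.

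The cost is some wording, possibly one CRF item, and slightly higher reported AE counts. The change affects reporting only; dosing and stopping rules stay as they are.

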9.4.5 BASELINE DESCRIPTIVE STATISTICS

Include content in this section if applicable, otherwise note as not-applicable.

Because all subjects will receive active intervention, Intervention groups will not be compared.

9.4.6 PLANNED INTERIM ANALYSES

No interim analysis is planned.

9.4.7 SUB-GROUP ANALYSES

No sub-group analyses are planned.

9.4.8 TABULATION OF INDIVIDUAL PARTICIPANT DATA

Individual participant data will not be listed by measure and time point.

1

9.4.9 EXPLORATORY ANALYSES

No exploratory analyses are planned.

10 SUPPORTING DOCUMENTATION AND OPERATIONAL CONSIDERATIONS

10.1 REGULATORY, ETHICAL, AND STUDY OVERSIGHT CONSIDERATIONS

10.1.1 INFORMED CONSENT PROCESS

10.1.1.1 CONSENT/ASSENT AND OTHER INFORMATIONAL DOCUMENTS PROVIDED TO PARTICIPANTS

Consent forms describing in detail the study intervention, study procedures, and risks are given to the participant and written documentation of informed consent is required prior to starting intervention/administering study intervention. The following consent materials are submitted with this protocol.: informed consent document.

10.1.1.2 CONSENT PROCEDURES AND DOCUMENTATION

Informed consent is a process that is initiated prior to the individual's agreeing to participate in the study and continues throughout the individual's study participation. Consent forms will be Institutional Review Board (IRB)-approved and the participant will be asked to read and review the document. The study coordinator and primary investigator will explain the research study to the participant and answer any questions that may arise. A verbal explanation will be provided in terms suited to the participant's comprehension of the purposes, procedures, and potential risks of the study and of their rights as research participants. Participants will have the opportunity to carefully review the written consent form and ask questions prior to signing. The participants should have the opportunity to discuss the study with their family or surrogates or think about it prior to agreeing to participate. The participant will sign the informed consent document prior to any procedures being done specifically for the study. Participants must be informed that participation is voluntary and that they may withdraw from the study at any time, without prejudice. A copy of the informed consent document will be given to the

participants for their records if requested. The informed consent process will be conducted and documented in the source document (including the date), and the form signed, before the participant undergoes any study-specific procedures. The rights and welfare of the participants will be protected by emphasizing to them that the quality of their medical care will not be adversely affected if they decline to participate in this study.

10.1.2 STUDY DISCONTINUATION AND CLOSURE

This study may be temporarily suspended or prematurely terminated if there is sufficient reasonable cause. Written notification, documenting the reason for study suspension or termination, will be provided by the suspending or terminating party to study participants, investigator, funding agency, the Investigational New Drug (IND) or Investigational Device Exemption (IDE) sponsor and regulatory authorities. If the study is prematurely terminated or suspended, the Principal Investigator (PI) will promptly inform study participants, the Institutional Review Board (IRB), and sponsor and will provide the reason(s) for the termination or suspension. Study participants will be contacted, as applicable, and be informed of changes to study visit schedule.

Circumstances that may warrant termination or suspension include, but are not limited to:

- Determination of unexpected, significant, or unacceptable risk to participants
- Demonstration of efficacy that would warrant stopping
- Insufficient compliance to protocol requirements
- Data that are not sufficiently complete and/or evaluable
- Determination that the primary endpoint has been met
- Determination of futility

Study may resume once concerns about safety, protocol compliance, and data quality are addressed, and satisfy the sponsor, IRB and/or Food and Drug Administration (FDA).]

10.1.3 CONFIDENTIALITY AND PRIVACY

- *Initials will be attached to data/samples*
- *Personally identifiable information will be released to third parties such as insurance carriers and primary physicians if warranted.*
- *Study coordinator, primary and sub-investigators will have access to records, data, and samples. Monitors or auditors outside of study investigators will need access as well.*

Participant confidentiality and privacy is strictly held in trust by the participating investigators, their staff, and the sponsor(s) and their interventions. This confidentiality is extended to cover testing of biological samples and genetic tests in addition to the clinical information relating to participants. Therefore, the study protocol, documentation, data, and all other information generated will be held in

strict confidence. No information concerning the study or the data will be released to any unauthorized third party without prior written approval of the sponsor.

All research activities will be conducted in as private a setting as possible.

The study monitor, other authorized representatives of the sponsor, representatives of the Institutional Review Board (IRB), regulatory agencies or pharmaceutical company supplying study product may inspect all documents and records required to be maintained by the investigator, including but not limited to, medical records (office, clinic, or hospital) and pharmacy records for the participants in this study. The clinical study site will permit access to such records.

The study participant's contact information will be securely stored at each clinical site for internal use during the study. At the end of the study, all records will continue to be kept in a secure location for as long a period as dictated by the reviewing IRB, Institutional policies, or sponsor requirements.

Study participant research data, which is for purposes of statistical analysis and scientific reporting, will be transmitted to and stored at Toyos Clinic. This will not include the participant's contact or identifying information. Rather, individual participants and their research data will be identified by a unique study identification number. The study data entry and study management systems used by the clinic site and research staff will be secured and password protected. At the end of the study, all study databases will be de-identified and archived at Toyos Clinic.

10.1.4 FUTURE USE OF STORED SPECIMENS AND DATA

Data collected for this study will be analyzed and stored at Toyos Clinic onsite at [name] or in appropriate storage facility where Toyos Clinic records are kept. After the study is completed, the de-identified, archived data will be transmitted to and stored at Toyos Clinic. for use by other researchers including those outside of the study.

When the study is completed, access to study data will be provided through Toyos Clinic.]

10.1.6 SAFETY OVERSIGHT

Safety oversight will be under the direction of an IRB and a Data and Safety Monitoring Board (DSMB) composed of individuals with the appropriate expertise, including studies and Acthar specifically.. Members of the DSMB should be independent from the study conduct and free of conflict of interest, or measures should be in place to minimize perceived conflict of interest. The DSMB will meet at least semiannually to assess safety and efficacy data on each arm of the study. The DSMB will operate under the rules of an approved charter that will be written and reviewed at the organizational meeting of the DSMB. At this time, each data element that the DSMB needs to assess will be clearly defined. The DSMB will provide its input to Toyos Clinic.

10.1.7 CLINICAL MONITORING

Clinical site monitoring is conducted to ensure that the rights and well-being of trial participants are protected, that the reported trial data are accurate, complete, and verifiable, and that the conduct of the trial is in compliance with the currently approved protocol/amendment(s), with International Conference on Harmonisation Good Clinical Practice (ICH GCP), and with applicable regulatory requirement(s).

- The primary investigator will conduct the monitoring on-site, once, for random review of certain data,, safety. Independent audits will not be conducted by <insert text> to ensure monitoring practices are performed consistently.]

10.1.8 QUALITY ASSURANCE AND QUALITY CONTROL

Each clinical site will perform internal quality management of study conduct, data and biological specimen collection, documentation and completion. An individualized quality management plan will be developed to describe a site's quality management.]

Quality control (QC) procedures will be implemented beginning with the data entry system and data QC checks that will be run on the database will be generated. Any missing data or data anomalies will be communicated to the site(s) for clarification/resolution.

Following written Standard Operating Procedures (SOPs), the monitors will verify that the clinical trial is conducted and data are generated and biological specimens are collected, documented (recorded), and reported in compliance with the protocol, International Conference on Harmonisation Good Clinical Practice (ICH GCP), and applicable regulatory requirements (e.g., Good Laboratory Practices (GLP), Good Manufacturing Practices (GMP)).

The investigational site will provide direct access to all trial related sites, source data/documents, and reports for the purpose of monitoring and auditing by the sponsor, and inspection by local and regulatory authorities.

10.1.9 DATA HANDLING AND RECORD KEEPING

10.1.9.1 DATA COLLECTION AND MANAGEMENT RESPONSIBILITIES

Data collection is the responsibility of the clinical trial staff at the site under the supervision of the site investigator. The investigator is responsible for ensuring the accuracy, completeness, legibility, and timeliness of the data reported.

All source documents should be completed in a neat, legible manner to ensure accurate interpretation of data.

Hardcopies of the study visit worksheets will be provided for use as source document worksheets for recording data for each participant enrolled in the study.

Clinical data (including adverse events (AEs), concomitant medications, and expected adverse reactions data) and clinical laboratory data will be entered onto the CRF provided by Toyos clinic.

10.1.9.2 STUDY RECORDS RETENTION

Study documents should be retained for a minimum of 2 years after the last approval of a marketing application in an International Conference on Harmonisation (ICH) region and until there are no pending or contemplated marketing applications in an ICH region or until at least 2 years have elapsed since the formal discontinuation of clinical development of the study intervention. These documents should be retained for a longer period, however, if required by local regulations. No records will be destroyed without the written consent of the sponsor, if applicable. It is the responsibility of the sponsor to inform the investigator when these documents no longer need to be retained.

